13. ALTERNATIVES TO STUDY PARTICIPATION

The alternatives to participation in this study are to not participate and to seek a program with another therapist or community program.

14. POTENTIAL RISKS

- 1). Potential risk of psychological assessments. For some participants, disclosing potential information about mental health symptoms and eating behaviors may be uncomfortable. Questions regarding individual behaviors, emotions or attitudes may be considered sensitive to some participants.
- 2). Potential risk of program. Weight loss program may result in discussions of sensitive or distressing topics (e.g., challenges, difficulties) which may provoke emotional responses. Further, participants will be encouraged to increase their level of physical activity. Improper or too-vigorous exercise or physical activity, if performed by the participant against the advice of the research staff, could be associated with injury or discomfort. Although increasing physical activity can have great benefits, participants may also experience some general fatigue or sore muscles or joints from being active. It is also possible that participants could fall or be injured in association with being physically active. Although engaging in physical activity improves overall health, it is also associated with some risks, such as injuries and rare sudden events (e.g., heart attack, sudden death related to heart problems).
- 3). Potential risk of loss of confidentiality: Risk associated with breach of confidentiality of behavioral research data. Since this study includes interviews, recorded data and audio recordings, there is a small potential that this information might not be kept confidential (for instance by theft of study material).

15. RISK MANAGEMENT PROCEDURES AND ADEQUACY OF RESOURCES

Risks of psychological assessments: Participants will receive consistent support from the study staff throughout the study. Participants will be told that they are free to choose not to answer any questions that may cause them distress if they wish.

For any unidentified/unreported psychiatric concerns identified during assessments for this project, we will execute the following protocol:

- 1. Participant will be notified of concerns identified.
- 2. Participant will be given a list of referrals in the community.
- 3. If significant concern is warranted (participant reports suicidal ideation, significant binging and purging), participants will be immediately assessed by the clinical staff or a licensed clinical psychologist present at the meeting regarding severity and an appropriate psychiatric referral will be made. If the assessment visit is held via ZOOM, a clinical staff member or licensed clinical psychologist will join the ZOOM meeting to assess the participant for severity. Participants experiencing significant psychological distress or discomfort will be discontinued from the protocol and referred for counseling with their consent. If suicidal ideation is reported, thorough suicide risk evaluation consisting of the assessment of past suicide attempts, plans,

availability of means, and current stressors to evaluate extent of risk will be conducted. A safety plan will be completed in collaboration with the participant and referrals will be made for therapy or to a crisis center. If the participant appears to be at imminent risk for suicide, the clinician will call 911.

Potential risk of program: Participants will receive consistent report from study staff. If significant distress occurs during program, they will be allowed to take a break from program and talk to one of the study staff. If suicidal ideation is reported the above protocol will be followed.

We will aim to enroll individuals in whom the level of activity recommended is highly unlikely to pose a medical problem. To address readiness, questions in the online screen and phone screen will be asked that evaluate whether participants have conditions in need of special monitoring (physical impairments, history of heart condition, doctor ever say can't do physical activity). The staff will be trained in appropriate guidelines, recommendations and advice relating to physical activity for a community-based program of this type, in order to minimize the likelihood of injury or discomfort. For patients who may be at higher risk due to medication or previous history (e.g., taking beta blockers, history of cardiac problems), clearance from their medical doctor may be required before starting program. In these cases, participants will sign a release form and the study team will contact the physician to see whether the physician agrees the participant can participate in the recommended level of activity (at least 150 minutes of moderate intensity exercise). If there is any concern for safety/readiness and physician approval cannot be obtained, participants won't be enrolled. Potential complications associated with moderate intensity exercise training at levels recommended by the CDC/ACSM are rare. However, subjects may find exercising uncomfortable and may experience sprains, other soft tissue injuries, or bone injuries.

Potential risk of loss of confidentiality: The research team will make every effort to keep any information confidential. Any study material will be stored in locked cabinets in UCSD sponsored facilities. Furthermore, a unique identification number will be used for each person in data sets and spreadsheets that do not readily identify a name. The identifying name information containing material will be locked and stored separately from data files. Any electronic files containing identifying information will be password protected and stored on Pediatrics secure servers with only appropriate study staff having access. The online screen will be collected as 2 separate surveys on REDCAP so that the identifying information is collected separately from the other screening responses linked by an ID number. Only study staff, who are trained in confidentiality and HIPAA will have access to the password protected identifying information and ID link. Accordingly, the online screen is submitted as 2 separate parts to delineate this separation. Similarly, the phone screen has been officially split into two documents. An ID number will be assigned and kept password protected with the identifying information only accessible to PI and designated study staff. Part 2 will be identified only with the ID number. Part 1 and Part 2 of the phone screens will be stored in separate locked filing cabinets.

Lastly, participants are informed of the option to complete all of the information on the online screen on the phone where they can provide the information.

To help maintain confidentiality of participants, if emailing more than one participant (e.g., emailing about reminder for program session), all participant's email addresses will be kept confidential by using the BCC function and no participant names will be included. When emailing participants from email templates, staff will copy from our templates instead of forwarding from emails sent to other participants and to always start new email documents to ensure no participant email information is accidentally disclosed to another participant.

Data Safety Monitoring Plan: Because of this low risk status, the data and safety monitoring plan (DSMP) for this trial focuses on close monitoring by the principal investigator (PI) and Drs. [name] and [name], the primary mentors, and [name], the safety officer, along with prompt reporting of excessive adverse

events and any serious adverse events to the NIH and to the IRB at the University of California, San Diego. Although the likelihood is low, there will be established procedures for monitoring and responding to adverse events resulting from moderate intensity physical activity. All participants will be given an instruction sheet at the start of the study that details what to do for common exercise-related injuries. Participants will be asked to reported injuries and health related problems that arise during program to the study PI. In the event of an injury requiring immediate assistance, the participant will be instructed to contact their primary care physician, and if necessary, go to the closest emergency center. All adverse events, UPRs or protocol deviations will be submitted to the IRB and the NIH as appropriate according to current policies. For Study 2, formal reports of adverse events will additionally be send to the safety officer.

Qualifications and responsibilities of the Safety Officer: The safety officer for study 2 will be [name], MS, MPH. [name] is an internal medicine physician at UCSD with an MPH in clinical effectiveness. [name] has an in depth understanding of the types and severity of comorbidities and injuries associated with adult obesity. As Safety Officer, [name] will review the reports sent by [name] or her study coordinator and will evaluate the information below presented to him to determine whether there is any corrective action, trigger of an ad hoc review, or stopping rule violation that should be communicated to the study investigator, the University of California San Diego IRB, and the NIDDK.

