6. SPECIFIC AIMS

Aim 1: Develop an initial treatment manual for NEXT.

Aim 2: Iteratively pilot NEXT on two cohorts of participants, and collect qualitative feedback which will be integrated into the NEXT program. (Study 1)

Aim 3: Determine feasibility and acceptability of NEXT (Study 1 & 2)

Exploratory Aim: Evaluate Mediators and Moderators of NEXT (e.g, depression, eating behaviors, self-efficacy)

Aim 4: Establish preliminary effects of NEXT on weight loss, executive function, and self-monitoring through a randomized-control trial comparing NEXT + behavioral weight loss (BWL) to BWL alone (Study 2)

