8. PROGRESS REPORT

Study 1 treatment materials were developed and recruitment of participants began in May 2019. The first group of 10 participants began baseline assessments in June 2019 and started in a 12-week pilot group in July 2019. The group program ended in October 2019 and 8 of 10 participants completed their post-treatment assessments thereafter. Some revisions were made to treatment materials based on feedback received from participants. Recruitment for the second pilot group began in September 2019 and participants completed baseline assessment visits thereafter. The second pilot group began group sessions in November 2019 and finished in February 2020 and 8 of 11 participants completed their post-treatment assessments.

Study 2 recruitment began in February 2020.

[name], the PI, has closely monitored the study. Recruitment has progressed according to plan for Study 1. There have been no formal reports given that no adverse events have occurred and all monitoring has been conducted by the PI and other internal team members.

Study 2 recruitment was recently completed.

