BWL includes daily self-monitoring of calorie intake and physical activity. Calorie goals will be shaped down to 1200-1400 calories for females and 1500-1700 for males. Physical activity recommendations will be consistent with guidelines suggesting a minimal of 150 minutes of at least moderate intensity activity each week with the ideal being >250 minutes. Lifestyle activity goals focus on building increased activity into typical, daily activities, such as walking or bicycling. Participants are also instructed to decrease sedentary behaviors, such as TV watching or computer usage outside of work. Participants will be encouraged to work toward achieving 10,000 steps per day. BWL will include elements of behavioral change recommendations including stimulus control, self-monitoring, goal setting, managing high-risk situations, meal planning, slowing eating, problem solving, social support, cognitive restructuring, lapse and relapse prevention skills, and maintaining weight loss.

Study 1: This is a study to aid in treatment development of a Novel Executive Function Treatment for Obesity (NEXT) and thus the design will be open label. After consenting to be a part of the study, participants will attend an in person assessment visit which will take approximately 3 hours. Then when enough people have completed assessments and meet inclusion criteria, they will attend a pilot program group (approximately 10-15 other adults). Group will meet weekly for 12 weeks and be scheduled for 75 minutes. There will be another inperson assessment that will take approximately 3 hours following the 12 weeks of pilot program groups.

Group programs will consist of 12 weekly, 75 minutes groups consisting of NEXT only, NEXT and BWL or BWL curriculum only.

Study 2 will consist of a randomized control trial. Study participants will consist of at least 64 adults who will be randomized to one of two conditions, one which will receive NEXT + BWL and one which will receive BWL alone. Each group will consist of 10-20 participants. Study participants will be blind to their condition. All groups will be twenty 75-minute sessions over the course of 6 months. Groups will be held inperson or via password-protected ZOOM meetings. If groups are held via ZOOM, on treatment nights, participants will be sent treatment materials and information on how to access the meetings via email.

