20. COMPENSATION FOR PARTICIPATION

Each study 1 participant will receive \$25 for the baseline assessment, and \$50 for the post-group assessment.

Each study 2 participant will receive \$50 for the mid-program assessment, \$100 for the post-program assessment, and \$150 for the 6-month follow-up assessment. Participants who withdraw, but who wish to have their weight measured or self-report their weight to study staff at follow-up time points will receive a \$25 gift card at each assessment time point (mid-program, post-program, and 6-month follow-up) that remains after the point which they withdrew. Participants who enroll and complete all assessment visits can earn up to \$300.

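### Study 2 offers only weight follow-up after formal withdrawal and does not say what follows discontinuation for distress, so executive function may go uncollected in both groups

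*Combined protocol and SAP*

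**What the plan says.** **Discontinuation.** Section 15, on the risks of psychological assessments, states: "Participants experiencing significant psychological distress or discomfort will be discontinued from the protocol and referred for counseling with their consent". It does not say whether later outcome assessments stop or go on. Further down, on the risks of the program, section 15 gives another response for participants distressed during the program: "they will be allowed to take a break from program".

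**Withdrawal.** Section 20 contains the only data collection after withdrawal that the protocol describes. It concerns "Participants who withdraw, but who wish to have their weight measured or self-report their weight to study staff at follow-up time points", who receive a $25 gift card at each remaining time point. The offer is voluntary and covers weight only. The section does not say whether someone discontinued by staff counts as having withdrawn.

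**Outcomes.** Aim 4 in section 6 is to "Establish preliminary effects of NEXT on weight loss, executive function, and self-monitoring" by a randomised comparison. EF stands beside weight there.

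**Schedule and analysis.** Section 9 gives each Study 2 participant four assessments (baseline, mid-program, post-program, 6-month follow-up) and attaches no attendance condition. Table 1 lists most EF tests at all four; the BRIEF is the exception at mid-program. Links to tasks and surveys that can be done online are emailed before the visit. The data analysis paragraph is written for the pilot and describes descriptive pre/post change. It defines no Study 2 analysis set and no missing-data method.

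**Study 1 retention.** Section 8 reports, for the first cohort, "8 of 10 participants completed their post-treatment assessments thereafter" and, for the second, "8 of 11 participants completed their post-treatment assessments". It gives no reasons for the losses.

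**The concern.** Section 20 recognises that outcomes of people who leave are worth having and pays to recover one of them, weight. No matching provision is made for EF, although part of the EF battery can be completed remotely. For people discontinued because of distress, even the weight offer is uncertain: staff could reasonably read section 15 as ending assessments together with the group program.

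Followed as written, this loses EF data that could have been collected. Fewer EF values mean a less precise comparison. If the reasons for leaving are related to EF change and differ between arms, the comparison of those still observed may no longer match the comparison of those randomised. With no missing-data method stated, nothing on the analysis side compensates.

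**Working it through.** The documents state no power calculation, dropout allowance or expected loss for Study 2, so there is no figure of the plan's own to reproduce.

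**Step 1: who is affected.**
- Stops attending sessions without withdrawing: section 9 still schedules all four assessments, and section 20 pays for assessments ($50, $100, $150), not for attendance. EF still appears due.
- Formally withdraws: section 20 offers weight only. EF is not sought.
- Discontinued for distress: section 15 is silent, and section 20 may or may not apply. Both EF and weight are unclear.

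**Step 2: Study 1 loss (section 8).**
- Cohort 1: 2/10 = 20.0%.
- Cohort 2: 3/11 = 27.3%.
- Pooled: (2 + 3)/(10 + 11) = 5/21 = 23.8%. The exact (Clopper-Pearson) 95% CI is 8.2% to 47.2%.

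This is all-cause non-completion of the post-treatment assessment.

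**Step 3: carried to Study 2 as an assumption.** Sections 9 and 10 plan at least 64 randomised. The number with post-program EF data is 64 × (1 − loss):
- at 23.8%: 64 × 16/21 = 48.8, about 49, so about 15 missing;
- at 8.2%: 64 × 0.918 = 58.8, about 59;
- at 47.2%: 64 × 0.528 = 33.8, about 34.

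**Step 4: precision.** With the same SD and equal proportional loss in both arms, interval width scales as 1/√n. The ratio is √(64/48.8) = 1.145, or about 15% wider. With 1:1 allocation (the ratio is not stated) this is √(32/24.4), the same value. Over the CI for the loss:
- √(64/58.8) = 1.04, about 4% wider;
- √(64/33.8) = 1.38, about 38% wider.

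The 15% is an upper figure for that loss, because a longitudinal model could use mid-program EF values from people lost later.

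**Step 5: what the fix could recover.** Recovered = about 15 × (share lost through withdrawal or discontinuation) × (share who accept the offer). Neither share is in the documents, so the answer lies anywhere from 0 to 15.

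**Step 6: bias.** In one arm, the mean among those observed differs from the full-arm mean by p × (mean of stayers − mean of leavers), where p is the loss. The bias in the treatment comparison is the difference between arms in that product. It is zero if loss and the stayer-leaver gap are equal in both arms. The documents give none of these terms, so no figure follows.

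**The case against.** The strongest case on the other side is that silence is not a rule. A reader might infer that participants discontinued by staff have no outcome follow-up. Section 15 does not say so, section 20 does not distinguish leaving by choice from leaving by staff decision, and the consent form, which may cover data after withdrawal, was not available for this review. That objection stands: the accurate statement is that follow-up after discontinuation is not specified.

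A reader might also infer that EF is sought from nobody who leaves, or that the EF result will rest on completers. Neither is supported. Non-attenders still appear due for assessment, no completer analysis is stated, and mid-program EF data exist for most tests.

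Nor is 24% an expected Study 2 loss. It comes from 21 people in an open-label pilot ("Group will meet weekly for 12 weeks and be scheduled for 75 minutes") with different payments, while Study 2 runs 20 sessions over 6 months and then a 6-month follow-up. Section 8 gives no reasons for the losses and reports no adverse events, so nothing ties any of them to the distress rule.

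The two responses to distress in section 15 might look contradictory. They sit under different headings, one for assessments and one for the program, and do not clearly conflict.

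Finally, remote collection is partial: Digit Span and the CVLT-Food are read aloud by staff. This limits the benefit of the fix but does not remove it. What survives all of this is that section 20 seeks weight and not EF after withdrawal, and section 15 leaves the matter open after discontinuation.

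**Conclusion.** The concern holds in a limited form. EF, a named Aim 4 outcome, is not sought after formal withdrawal from Study 2 and may not be sought after discontinuation for distress. This goes beyond missing detail, because following the text as written forgoes data that could be collected.

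If all-cause loss matched Study 1, about 49 of 64 would have post-program EF data and the interval would be up to about 15% wider. This rests on carrying 5/21 over to a longer, randomised program and on equal proportional loss in both arms. It measures all loss, not the part caused by this gap, and that part could be small. A reader might want to attach a bias in SD units, but that would need assumed values for every term. The point is a low-cost improvement, not a threat to the trial's validity.

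**What to change.** - **Section 20:** extend the optional follow-up for participants who withdraw to include the EF questionnaires and computer tasks that can be completed online, at the remaining time points.
- **Section 15:** state whether being discontinued ends the group program only or data collection too. Where staff judge it appropriate and the participant consents, make the same optional offer.
- **Analysis:** state that all available data are analysed in the randomised arm.

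The cost is about a sentence in each place and use of the links already emailed. The study team would need to decide whether the $25 gift card, now given for a weight, suits a longer contact. The downsides are optional contact with people who have left, and recovery of only the online part of the EF battery. Section 8 says Study 2 recruitment was recently completed, so the change helps only with assessments still due. No change to the clinical response to distress is proposed.

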Assessment measures are specified below but assessments will occur at two additional time points for a total of four assessments per participant: baseline, at mid-program (take place approximately between sessions 10-14), post program, and 6 month follow-up. Assessment visits will be held in-person or in password-protected ZOOM meetings. Links for assessment tasks that can be completed online including computer tasks and surveys will be emailed to the participant before the assessment appointment with instructions on how to access the ZOOM meeting.

Table 1. Measurement table and assessment time-points for study 2:

	Instrument	Baseline	During group visits	Mid- program	Post- Program	6-month f- up
Anthropometry	Height/Weight	Х	Х	Х	Х	Х
	WRAT-4	Х				
Screening Measures	MINI	Х			Х	x
	Medical and medications	X		Х	Х	Х
Binge Eating	EDE	Х		Х	Х	Х
	EDEQ	Х	Х	Х	Х	X
	DKEFS	X		Х	Х	X
Executive Function	BRIEF	Х			Х	X
	PSI	Х		Х	Х	X
	Delay Discounting	X		X	X	Х
	Brain Health Index	X		Х	Х	X
	DFLEX	Х	X	Х	Х	х
	Digit Span	X		Χ	Х	Х
	WCST	X		Х	Χ	×
	CVLT- Food	X	X	X	Χ	×
	Stop Signal Task	X	X	Χ	X	X
	Tower of London	X	X	Χ	X	Х
	ТМТ	X	X	Х	Х	х
	СРТ	Х		Х	Х	Х
	PHQ-9	Х		X	X	х
	DERS	Х		Х	Х	х
Questionnaires psychiatric	GAD-7	X		Х	Х	х
Questionnaires stress	PSS	Х		Х	Х	×
Questionnaires eating behavior	YFAS 2.0	Х		Х	Х	х
	EAH	X		X	X	X
	Adult Eating Behavior Questionnaire (AEBQ)	Х		Х	Х	Х

	Reward Based Eating Drive Scale (RED)	Х		х	Х	Х
Questionnaires impulsivity	S-UPPS-P	Х	Х	Х	X	X
Questionnaires-self-efficacy	General Self Efficacy Scale	Х	Х	Х	Х	Х
Questionnaires other health behaviors	GPAQ	Х		Х	Х	Х
	Godin leisure time exercise questionnaire	X	X	X	X	X
	Q-LES-Q-SF	Х	Х	Х	Х	X
Adherence	ADH	Х		Х	Х	X
	BWL	X		X	X	×
Feasibility/Acceptability	Attendance		Х	Х	Х	Х
	Acceptability survey		X	X	X	×
Self-Monitoring	Habit books		Х			

Measurements

Screening Measures (baseline only): Participants will complete the Mini-International Neuropsychiatric Interview (MINI)²⁹ to confirm eligibility (i.e., absence of exclusionary psychiatric condition). The WRAT³⁰ reading assessment will be administered at baseline to evaluate reading level and ensure valid administration of the assessments.

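### For injuries and other physical health problems, the only stated way of finding adverse events is a participant's own report to the PI during the program; the medical review scheduled through 6 months is not linked to adverse event recording.

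*Combined protocol and SAP*

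**What the plan says.** Section 15, Data Safety Monitoring Plan, tells participants what to do about physical problems: "Participants will be asked to reported injuries and health related problems that arise during program to the study PI". It adds that "there will be established procedures for monitoring and responding to adverse events resulting from moderate intensity physical activity". What it then describes is an instruction sheet on common exercise injuries, this request to report, and advice on where to seek care. Onward reporting is covered: "All adverse events, UPRs or protocol deviations will be submitted to the IRB and the NIH as appropriate according to current policies". The safety officer is an additional recipient of formal adverse event reports in Study 2.

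Psychiatric concerns are handled differently. Section 15 provides a staff-detected route: "For any unidentified/unreported psychiatric concerns identified during assessments for this project, we will execute the following protocol". Section 9 (Data collection protocol) adds an automatic email alert for suicidal ideation or self-harm items in surveys completed at home, checked each business day.

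Study 2 has four assessments: "baseline, at mid-program (take place approximately between sessions 10-14), post program, and 6 month follow-up". Table 1 lists "Medical and medications" at all four. The Measurements text does not describe the content of that item or say where its findings go.

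Section 14 warns that "participants may also experience some general fatigue or sore muscles or joints from being active" and mentions falls and injuries. Section 15 mentions sprains and soft tissue or bone injuries, and calls complications of moderate exercise rare. On Study 1, Section 8 states: "There have been no formal reports given that no adverse events have occurred".

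**The concern.** A count of harms can be interpreted only if the reader knows who was asked, what was asked and over what period. For physical events the plan relies on the participant to start the report, and its stated window closes when the program does. Participants remain under observation until the 6-month follow-up, after being encouraged to build up their physical activity.

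Two things are at stake. The safety officer is asked to decide on corrective action, ad hoc review and stopping-rule violations, and prompt reporting of excessive adverse events is promised; both need counts gathered in a known and uniform way. In addition, a later statement that no adverse events occurred could not be told apart from one in which events went unreported.

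**Working it through.** The documents give no adverse event rate, capture rate or harms analysis, so there is no figure of the plan's own to reproduce. The check is mainly textual.

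**Step 1. Routes by type of event**

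| Type of event | Stated route | Stated window |
|---|---|---|
| Injury or other physical problem | Participant reports to the PI (Section 15) | During the program |
| Psychiatric concern | Staff detection at assessments (Section 15) | Any assessment |
| Suicidal ideation or self-harm items | Survey alert (Section 9) | Surveys completed at home |
| Medical and medication review | Scheduled in Table 1, content not described, no link to adverse event recording | Baseline, mid-program, post-program, 6 months |

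The gap lies between the first row and the last. A scheduled contact at which staff could ask already exists at three post-baseline visits, but the plan does not say that it feeds an adverse event log.

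**Step 2. Time outside the stated window.** Study 2 sessions run over 6 months. If the 6-month follow-up is counted from the end of the program (an assumption, although Table 1 lists it after the post-program visit), the share of observation outside the window is 6 / (6 + 6) = 50%.

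**Step 3. What the pilot's zero can show.** Inputs from Section 8: 10 + 11 = 21 starters; 8 + 8 = 16 with post-treatment assessments; 0 events. The exact upper limit for zero events in n people is 1 − α^(1/n).

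- n = 21: 1 − 0.05^(1/21) = 0.133 (one-sided 95%); 1 − 0.025^(1/21) = 0.161 (upper limit of two-sided 95%).
- n = 16: 1 − 0.05^(1/16) = 0.171; 1 − 0.025^(1/16) = 0.206.

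These limits assume full capture. They reflect the small sample, not the reporting method.

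**Step 4. Effect of incomplete capture (illustration only).** Let p be an assumed true per-person rate and c an assumed share of events reported. The chance of recording none in 21 is (1 − pc)^21.

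- p = 5%, c = 100%: 0.95^21 = 0.34.
- p = 10%, c = 100%: 0.90^21 = 0.11.
- p = 10%, c = 50%: 0.95^21 = 0.34.
- p = 10%, c = 25%: 0.975^21 = 0.59.

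Expected recorded cases in Study 2 with 64 participants are 64 × p × c:

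| p | c = 100% | c = 50% | c = 25% |
|---|---|---|---|
| 10% | 6.4 | 3.2 | 1.6 |
| 5% | 3.2 | 1.6 | 0.8 |

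The values 5% at full capture and 10% at half capture give the same chance of a zero pilot count (0.34). The zero therefore cannot separate a low rate from low capture.

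**The case against.** The strongest reply is that this is a low-risk behavioral trial whose safety net is wider than one sentence. Participants are instructed to report, not merely left free to do so. Psychiatric harms have two staff-side routes. The 6-month visit includes the medical review, the MINI and the PHQ-9, and the medical review may already ask about new problems, since its content is not shown. Monitoring procedures for exercise-related events are promised, though not described. All of this stands, and it confines the point to physical events and to a missing link rather than a missing visit.

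A reader might infer several stronger things that the documents do not support:

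- *That zero pilot events show nobody asked.* At a 5% true rate with full capture, zero in 21 would occur 34% of the time. The protocol says such problems may occur and calls complications rare. It does not say whether ordinary soreness counts as an adverse event. Section 9 allows Study 1 groups to be NEXT only, BWL only or both, so the pilot's exposure to the activity recommendation is not established.
- *That comparisons of harms between arms would be biased.* Both arms receive BWL, the same session schedule and the same assessments, and participants are to be blind to condition. No mechanism for differential reporting is shown, and no comparison of harms is planned.
- *That harms will be under-counted.* No capture rate is given, so only *may* is supportable.
- *That the safety officer sees only volunteered events.* Section 15 refers to information listed below it, but no list appears in the text available. It may have been lost in extraction.

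On timing, Section 8 says Study 2 recruitment is complete. Questions added now could be asked at some visits and not others. That is a real cost, and the fix has to deal with it.

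**Conclusion.** The point holds for injuries and other physical health problems. Their only stated ascertainment is a participant-initiated report to the PI, limited to the program period, and the medical review scheduled at three post-baseline visits is not linked to adverse event recording. Physical events may be missed, most plausibly after the program ends. The safety officer's review of such events would rest on counts not gathered by a uniform method.

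The size of any under-count cannot be determined; the capture rates used above are assumptions. What can be stated is that the pilot's zero does not exclude a true rate of 13% (one-sided) or 16% (two-sided), and so should not be offered as evidence of safety. The conclusion assumes that no separate procedure outside these documents already supplies a standard inquiry. It is a minor, inexpensive improvement and does not affect the efficacy aims.

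**What to change.** - At the remaining mid-program, post-program and 6-month contacts, add a short fixed question set to the existing medical and medication review: injury, new or worse medical problem, and emergency visit or hospital stay since last contact.
- Use the same wording in both arms. Also ask withdrawn participants who agree to the follow-up weight contact described in Section 20; that section now covers weight only, so the wider contact needs to be added to the protocol.
- Enter the answers in the adverse event log and send counts by arm to the safety officer.
- Report solicited events separately from spontaneously reported ones, and state which visits and cohorts were asked.
- If no contacts remain, describe the ascertainment method beside any harms result. In either case, do not present the pilot's zero as evidence of safety.

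The cost is a few items on a form already in use, a protocol amendment, and more minor events to log. Ascertainment will be uneven if some visits are already done, which is why solicited and spontaneous events must be kept apart.
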